14.3 Serious Adverse Events reporting rules

All events that meet one or more criteria of seriousness (see Section 13.1.2.) will be reported **continuously** from the date of informed consent signature to 28 days after the last study drug administration of the maintenance period. During maintenance on-demand, if GA101 is discontinued (temporarily or permanently), SAEs will be reported until 28 days after last study drug administration. If GA101 is reintroduced (according to MRD results), SAEs will further be reported according to the same reporting rules.

SAE will be reported regardless:

- the relationship to the study treatment
- the administration of new lymphoma therapy,
- disease progression.

Nevertheless, the following SAEs that occur during maintenance on-demand beyond 28 days after the last administration of GA101 will be reported as SAEs regardless relationship to study treatment:

- Death
- Life-threatening events
- Severe infections, hepatitis, progressive multi-focal encephalopathy
- Cardiac events
- Neutropenia

To note that all SAEs **considered related to the study medication** will **always** be reported even if occur beyond 28 days after the last administration of GA101 including during the follow-up period.

Whenever possible, symptoms should be grouped as a single syndrome or diagnosis. The investigator should specify the date of onset, intensity, action taken regarding the study medication, corrective therapy given, outcome of all SAEs and his/her opinion as to whether the SAE can be related to the IMP.

General SAE reporting rules:

- Any episode of any grade of toxicities, which meets one of the seriousness criteria must be reported as "Serious Adverse Event" in the appropriate SAE form
- Signs, symptoms and physical findings indicative of lymphoma or progression of lymphoma are not to be reported as "Serious Adverse Event"
- Hospitalizations **not to be considered** as SAE are:
 - Planned hospital admissions or surgical procedures for an illness or disease which existed before the patient was enrolled in the study or before the study drug was given are not to be considered SAEs unless the condition deteriorated in an unexpected manner during the study (eg surgery was performed earlier than planned).
 - A procedure for protocol therapy administration or protocol/disease-related investigations. Hospitalization or prolonged hospitalization for a complication will be reported as an SAE
 - Routine treatment (e.g. administration of blood or platelet transfusion) or monitoring of the studied indication (e.g., surgery, scans, endoscopy, sampling for laboratory tests, bone marrow sampling) not associated with any deterioration in condition. Hospitalization or prolonged hospitalization for a complication remains a reportable SAE

- Hospitalization or prolongation of hospitalization for technical, practical, or social reasons, in absence of an AE
- Emergency outpatient treatment or observation that does not result in admission (unless considered as an important medical or life-threatening event)

14.3.1 ***Obligations of the investigator***

In a case of SAE the investigator must immediately (within 24 hours):

- **Complete SAE form with all relevant information regarding SAE**
- **SEND the SAE pages to**

LYSARC Pharmacovigilance department

[contact]

Email: [contact]

All SAE forms must be dated and signed by the responsible Investigator or one of his/her authorized staff Members.

- May attach the photocopy of all examinations carried out and the dates on which these examinations were performed. Care should be taken to ensure that the patient's identity is protected and the patient's identifiers in the Clinical study are properly mentioned on any copy of source document. For laboratory results, include the laboratory normal ranges.
- Follow up of any SAE that is fatal or life-threatening should be provided within one calendar week.

For SAEs, the following must be assessed: relationship to each study drug, action taken, and outcome to date. The assessment of whether there is a reasonable possibility of a causal relationship is usually made by the investigator; it can be one of two possibilities:

- Unrelated (no reasonable possibility)
- Related. (reasonable possibility)

Items to be considered when assessing the relationship of a SAE to the study drug are:

- Temporal relationship of the onset of the event to the initiation of the study drug
- The course of the event, considering especially the effect of discontinuation of study drug or reintroduction of study drug, as applicable
- Whether the event is known to be associated with the study drug or with other similar treatments
- The presence of risk factors in the study subject known to increase the occurrence of the event
- The presence of non-study drug-related factors which are known to be associated with the occurrence of the event.

14.3.2 ***Obligations of the Sponsor***

During the course of the study, the Sponsor will report in an expedited manner all SAEs that are both unexpected and at least reasonably related to study drugs, to the EMA, Health Authorities, Ethic Committees in each country in accordance with international and local regulations, and to the Investigators. The causality assessment given by the investigator should not be downgraded by the sponsor. If the sponsor disagrees with the investigator's causality assessment, the opinion of both the investigator and the sponsor should be provided with the report.

The expectedness of a serious adverse reaction will be determined by the Sponsor according to the reference safety information (Investigator's Brochure) of the study drugs.

LYSARC Pharmacovigilance department will report all safety information from the trial in the Development Safety Update Reports and will notify the reports to the Health Authorities and Ethics Committees in accordance with international and local regulations.

14.4 Follow up of AEs and SAEs

Any SAE should be monitored until it is resolved or is clearly determined to be due to a patient's stable or chronic condition or underlying condition. Any additional information known after the event has been initially reported should be sent to LYSARC as soon as information becomes available.

All AEs must be documented and the outcome must be followed-up until the return to normal or consolidation of the patient's condition.

Subjects who prematurely discontinued study treatment due to any AE will be followed at least until the outcome is determined even if it implies that the follow-up continues after the patient has left the trial.

14.5 Adverse Events of Special Interest

The following AE is considered as of special interest and require attention from investigator if occurring. In addition, they have to be reported immediately in the eCRF, irrespective of the seriousness criteria, and whatever the grade:

- **TLS** (tumor lysis syndrom)
- **IRR** grade 4 occurring during or within 24 hours after the GA101 infusion

They have to be signaled to sponsor using the dedicated form:

LYSARC [contact]
Email: [contact]

14.6 Pregnancy

14.6.1 **Females of Childbearing Potential**

Pregnancies and suspected pregnancies (including a positive pregnancy test regardless of age or disease state) of a female subject occurring while the subject is on study drug, or within 28 days of the subject's last dose of study drug, are considered events to be reported immediately to LYSARC Pharmacovigilance on the appropriate Pregnancy Form.

LYSARC [contact]
Email: [contact]

If the subject is on study drug, the study drug is to be discontinued immediately and the subject instructed to return any unused portion of the study drug to the Investigator.

The exposure of any pregnant female (e.g. caregiver or pharmacist) to study drug is also an immediately reportable event.

The female should be referred to an obstetrician/gynecologist preferably one experienced in reproductive toxicity for further evaluation and counseling.

The Investigator will follow the female subject until completion of the pregnancy, and must notify LYSARC immediately about the outcome of the pregnancy (either normal or abnormal outcome).

If the outcome of the pregnancy is abnormal (i.e., spontaneous or therapeutic abortion) the Investigator should report the abnormal outcome as an AE. If the abnormal outcome meets any of the serious criteria, it must be reported as an SAE within 24 hours of the Investigator's knowledge of the event using the SAE Report Form, or approved equivalent form.

All neonatal deaths that occur within 28 days of birth should be reported, regardless of causality, as SAEs. In addition, any infant death after 28 days that the Investigator(s) suspects to be related to the in utero exposure to the study drug should also be reported to LYSARC within 24 hours of the Investigator's knowledge of the event using SAE form.

14.6.2 **Male patients**

If a female partner of a male patient taking the study drug becomes pregnant, the male patient taking the study drug should notify the Investigator, and the pregnant female partner should be advised to call her healthcare provider immediately.

If a pregnancy related event is reported in a female partner of a male subject, the investigator should determine whether the female partner is willing to release her medical information to LYSARC Pharmacovigilance and allow the pregnancy related event to be followed-up to completion.

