Exclusion Criteria	
 • Severe cardiac disease: NYHA grade 3-4 • Impaired liver (ALAT/ASAT ≥ 2.5ULN, bilirubin ≥ 1.5ULN), renal (calculated creatinine clearance < 50ml/min) or other organ function which will interfere with the treatment, if not related to lymphoma. • History of chronic liver disease • Hepatic veno-occlusive disease or sinusoidal obstruction syndrome • Any of the following laboratory abnormalities, if not result of a BM infiltration: 
 - Absolute neutrophils count (ANC) $<1,500 /mm^3$ ($1.5 \times 10^9/L$) - Platelet counts $< 75,000/mm^3$ ($75 \times 10^9/L$) • Pregnancy/Nursing mothers • Fertile men or women of childbearing potential unless: 
 - surgically sterile or ≥ 2 years after the onset of menopause - willing to use a highly effective contraceptive method (Pearl Index <1) such as oral contraceptives, intrauterine device, sexual abstinence or barrier method of contraception in conjunction with spermicidal jelly during study treatment and in female patients for 18 months after end of antibody treatment and in male for the duration of the treatment and after the last dose administered in accordance with the SmpC of the different products administered • Patients with a malignancy that has been treated but not with curative intent, unless the malignancy has been in remission without treatment for ≥ 5 years prior to enrollment. Patients with a history of curatively treated basal or squamous cell carcinoma or melanoma of the skin or in situ carcinoma of the cervix are eligible. • Known seropositivity for HIV, HCV or other active infection uncontrolled by treatment.

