Safety consideration	
Time of Analysis
 
Given the fact that primary endpoint is prematurely determined in study treatment period, 2 types of analysis will be performed:
 
 • Primary criterion analysis • Final analysis 
Primary criterion analysis:
 
Primary criterion analysis will be performed once all patients included in efficacy set (70 evaluable patients) have completed 4 cycles of treatment or treatment discontinued prior to cycle 4 of the study and will consist of analyzing:
 
 • Primary criterion : MRD rate in bone marrow after the 4 cycles or at treatment discontinuation of GA-DHAP • Treatment exposure • Stem cell collection failure • Secondary safety endpoints 
Final analysis:
 
All analyses will be performed when all included patients will have performed the end of treatment visit (end of maintenance “on demand” period or treatment discontinued from the study).
 
 • AE of grade 3-5 (CTCAE – v 4.03) regardless the relationship to IMP occurring from the date of informed consent signature, and up to 28 days after last treatment administration, will be recorded on the AE pages of eCRF. • Some adverse events which are attributable to the ASCT procedure only and not to the study drug are not to be entered in the eCRF (listed in section 14.2). • Any grade for AESI will be collected from ICF signature and until 28 days after last treatment administration regardless the relationship to IMP • All events that meet one or more criteria of seriousness, regardless the relationship to IMP, occurring from the date of the informed consent signature, during treatment administration period and up to 28 days after last drug administration, will be reported as SAE.

	
A SAE that occurs after this time, including follow up period, will be reported if considered related to IMP.
 
In a case of SAE the Investigator must immediately (within 24 hours):
 
SEND the SAE pages to LYSARC Pharmacovigilance department: [contact] OR EMAIL TO [contact]
 
Pregnancy and suspected pregnancy will be reported on Pregnancy Form to LYSARC PV from the date of informed consent signature and up to 28 days after the last study drug administration.

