9.9 End of treatment and premature treatment discontinuation evaluations

Patients will be evaluated within 28 days of end of last injection or following premature treatment discontinuation

- Physical examination
- ECOG PS
- Blood cell counts: Hemoglobin, leukocyte count, neutrophils, lymphocytes, platelets and lymphoma cells
- Bone marrow aspiration and biopsy if positive at previous evaluation according to local diagnosis
- Cervical, Chest, abdomen and pelvis CT scan IV contrast
- Evaluation of the disease response (Cheson 1999)
- Any other evaluations or procedures performed at baseline for evaluation of the disease response
- Adverse events
- **Samples for MRD study** : blood sampling and BM aspiration

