9.10 Follow-up assessments

The patients mentioned below will be in follow-up, if possible until death up to the end of the study:

- the patients who complete the first 3 years of maintenance and whose MRD was not informative at baseline
- the patients who discontinue the study treatment
- the first patients who complete the 6 years of maintenance

Thereafter, the long term follow-up of patients will be organized for further analysis.

The following assessments must be conducted every 3 months during the first 2 years, then every 6 months until the last visit of the last patient.

9.10.1 Patients who have discontinued treatment due to reasons other than progressive disease or relapse (meaning patients who did not experienced progression or relapse)

The following parameters will be assessed:

- Physical examination
- ECOG PS
- Blood cell counts: Hemoglobin, leukocyte count, neutrophils, lymphocytes, platelets and lymphoma cells
- Thorax, abdomen and pelvis CT with IV contrast every year
- Any other evaluations or procedures for evaluation of the treatment response.
- Evaluation of the treatment response (Cheson 1999: **see Appendix 8** "Response criteria for lymphoma")

Patients included in the study who withdraw before study treatment start will not be followed.

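### Pregnancy Form reporting for female patients ends 28 days after the last dose, although the protocol requires contraception for 18 months

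*Protocol*

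**What the plan says.** **Reporting.** Protocol 14.6.1 requires the Pregnancy Form for pregnancies and suspected pregnancies of a female patient "occurring while the subject is on study drug, or within 28 days" of her last dose. The safety part of the synopsis gives the same end point, with reporting running "from the date of informed consent signature and up to 28 days after the last study drug administration". Section 14.6.1 then asks the investigator to follow the woman until the pregnancy ends and to notify the outcome, whether normal or abnormal.

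**Contraception.** The exclusion criteria, in the synopsis and in 8.2, admit fertile women only if they are willing to use highly effective contraception during treatment and "in female patients for 18 months after end of antibody treatment".

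**Outcomes.** Two further rules in 14.6.1 are worded without a limit counted from the last dose: "If the outcome of the pregnancy is abnormal (i.e., spontaneous or therapeutic abortion) the Investigator should report the abnormal outcome as an AE" and "All neonatal deaths that occur within 28 days of birth should be reported, regardless of causality, as SAEs". The section also asks for later infant deaths that the investigator suspects are linked to in utero exposure.

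**Late serious events.** Section 14.3 keeps related serious adverse events (SAEs) reportable beyond 28 days, including in follow-up. Section 14.1.2 lists a congenital anomaly or birth defect as a criterion of seriousness.

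Each of the two time limits appears twice and consistently, so neither looks like a typing or extraction error. Nothing in the protocol or SAP extends Pregnancy Form reporting past 28 days.

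**The concern.** By asking for 18 months of contraception, the protocol treats that period as one in which pregnancy should be avoided after obinutuzumab. A woman who conceives in month 3 is pregnant in that period, yet 14.6.1 as written does not require the site to tell the sponsor or to follow her.

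What is at stake is knowledge of pregnancy outcomes after recent exposure. If only bad outcomes judged related arrive later, they arrive without a denominator: normal outcomes and the pregnancies themselves are not collected.

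The clearest case is a woman who stops treatment permanently without progression, or one of "the patients who complete the first 3 years of maintenance and whose MRD was not informative at baseline". Section 9.10 keeps her under observation: "The following assessments must be conducted every 3 months during the first 2 years". The site may therefore learn of a pregnancy that it has no duty to report.

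**Working it through.** The plan gives no figure of its own on this point. The check compares the windows and does date arithmetic, with 1 month = 30.44 days.

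**1. The gap between the windows**
- Contraception after the last dose (synopsis, 8.2): 18 × 30.44 = 548 days.
- Pregnancy Form reporting after the last dose (synopsis, 14.6.1): 28 days.
- Uncovered: 548 − 28 = 520 days; 520 / 30.44 = 17.1 months; 520 / 548 = 94.9%.

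**2. What is still reportable after day 28**

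| Event | Rule | Reportable? |
|---|---|---|
| Pregnancy beginning by day 28, found later | 14.6.1 speaks of occurrence, not detection | Yes |
| Birth defect or other SAE judged related | 14.1.2, 14.3 | Yes |
| Later infant death suspected to be due to in utero exposure | 14.6.1, no limit from last dose | Yes on its wording |
| Abortion or neonatal death after a pregnancy beginning past day 28 | 14.6.1, no limit from last dose, but in a section triggered by the 28-day window | Ambiguous |
| The late pregnancy itself, or one with a normal outcome | None | No |

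**3. Would the site see the patient?** Take a woman followed under 9.10 without progression, with visits every 3 months (91.3 days). The protocol does not say from when the interval is counted, so both options are shown.
- From the last dose: days 91, 183, 274, 365, 457, 548, which is 6 visits.
- From an end-of-treatment visit at day 28: days 119, 211, 302, 393, 485, which is 5 visits (the sixth, day 576, is past day 548).

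All of these fall after day 28. At most the end-of-treatment evaluation lies inside the reporting window (9.9: "Patients will be evaluated within 28 days of end of last injection or following premature treatment discontinuation").

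**4. Do the 18 months fit inside the trial?** This uses the last-enrolled patient, with no treatment delays. Study end is 6.5 × 12 = 78 months after last inclusion (Protocol 7).
- Cycle 1 day 1 to cycle 4 day 1: 63 days. To the start of conditioning: 28 to 56 days. Conditioning: 8 days. Total 99 to 127 days, or 3.3 to 4.2 months.
- Add 2 to 3 months to the start of maintenance and 36 months of maintenance: 41.3 to 43.2 months from cycle 1 day 1.
- Inclusion to cycle 1 day 1, assumed 0 to 40 days (28-day baseline window, plus up to 12 days for COP and the 1-week gap): the last maintenance dose falls 41.3 to 44.5 months after inclusion.
- Room left after that dose: 78 − 44.5 = 33.5 to 78 − 41.3 = 36.7 months. Both exceed 18.

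For on-demand doses the result differs. The on-demand phase ends at 41.3 + 36 = 77.3 to 44.5 + 36 = 80.5 months on this schedule. The 18 months fit only if the last dose comes by month 78 − 18 = 60. Earlier enrolees have more room, by up to the roughly 2-year recruitment period: for the first enrolled, about 60 + 24 = month 84, beyond the end of the on-demand phase.

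**5. Off-drug intervals in the on-demand phase.** Protocol 7 lists this phase within the treatment period, while the 28 days run from a dose. Section 14.3 gives a stop-and-restart rule, but for SAEs only. Whether an MRD-negative woman between courses counts as on study drug is not stated.

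**The case against.** The strongest case against is that nothing is inconsistent. The 28 days match the general windows for adverse events (14.2) and SAEs (14.3). The 18 months are an eligibility condition about willingness to use contraception. No statement in the documents says that reporting must last as long as contraception. That stands: a reader might infer a contradiction between the two rules, but they impose different duties and can both be followed. The point is about safety information forgone, not an error.

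A reader might also infer that all late harm goes unreported. The documents do not support that, as the table under step 2 shows. The backstops are still partial. The related-SAE route needs a judgement of relatedness, every route needs the investigator to learn the outcome, and the duty to follow to completion sits under the 28-day trigger.

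The figure of 520 of 548 days measures calendar time, not consequence. That is correct, and the consequence cannot be quantified from the documents.

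The objections on cost and yield also stand. After progression, 9.10.2 records only survival status and other malignancies. Pregnancy tests are scheduled at baseline only, and the follow-up list has neither a test nor a question. Late on-demand doses can push the 18 months past study end. Changing the window therefore needs a rule for study end and cannot promise full capture.

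On the off-drug intervals, a reader might infer a demonstrated hole. The documents support only an ambiguity: if the phase counts as treatment, such pregnancies are already reportable; if it does not, 28 days from the last dose applies.

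**Conclusion.** The point holds as a cheap, optional improvement to safety reporting. About 17 of the 18 months after the last dose in which the protocol requires contraception carry no duty to report or follow a pregnancy as such. What is certainly lost is the late pregnancy itself, a normal outcome, and systematic follow-up to completion. Related SAEs and suspected exposure-related infant deaths are not lost.

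No endpoint, decision rule, error rate or analysis set is affected. The number of women of childbearing potential is not given. That it is small is an assumption; the SAP's baseline table of childbearing status (Appendix 7.1) would show it. The visit counts assume follow-up without progression, and the trial-end calculation assumes no treatment delays and 0 to 40 days from inclusion to cycle 1.

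**What to change.** In 14.6.1 and the synopsis, require the investigator to report on the existing Pregnancy Form any pregnancy in a female patient that he or she becomes aware of, if it occurs during treatment or within 18 months after the last obinutuzumab dose, and to follow it to outcome. State that off-drug intervals of the on-demand phase count as treatment for this purpose. Inside that window the ambiguity of the abnormal-outcome sentences no longer matters.

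Add one sentence on windows that outlast the study. Either reporting continues on awareness, as 14.3 already does for related SAEs, or it stops at study end. Either is workable if stated.

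The cost is a change of wording in two places, the study-end sentence, and a little more pharmacovigilance work to follow any late pregnancy. No visit, test or form is added. For that reason capture will stay incomplete for women who have progressed and for women given late on-demand doses, and elsewhere it depends on the site being told.
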